## Power Analysis

An *a priori* power analysis was used to determine that we require eighteen or more participants to achieve 80% power to reject the null hypothesis, which states there is no difference between pre-test (noFES) and post-test (FES) conditions in a pairwise comparison with a significance level (alpha) of 0.05. An effect size of 0.7 was used for the power analysis based on a previous study of FES impact on post-stroke participants.

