## Reported Outcomes

For each metric of interest, we will take the average of each participant's metric values across steps for both noFES and FES walking. We will also report the 95% confidence interval for the differences between FES and noFES outcome metrics.

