## Tests of Statistical Significance

The Shapiro-Wilk test for normality will be used to assess the assumption of normality. If the outcome variable is approximately normally distributed, a paired t-test will be used to statistically compare noFES and FES outcome metrics. If the normality assumption is not met, the Wilcoxon signed rank test will be used as an alternative to the paired t-test for this statistical comparison. Bonferroni multiple hypothesis correction will be utilized (four outcome metrics), and our corrected significance level for comparison is 0.0125 (0.05 divided by the four hypotheses tested).

 N. Kapadia, B. Moineau, and M. R. Popovic, "Functional Electrical Stimulation Therapy for Retraining Reaching and Grasping After Spinal Cord Injury and Stroke," *Front. Neurosci.*, vol. 14, p. 718, Jul. 2020, doi: 10.3389/fnins.2020.00718.

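### The single-step Bonferroni test at 0.0125 is valid, but Holm's step-down procedure would give more power per metric at no cost when two or more metrics respond

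*SAP*

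**What the plan says.** The SAP compares walking with and without stimulation on four metrics, using a paired t-test, or the Wilcoxon signed rank test if normality fails. On multiplicity, Tests of Statistical Significance says "Bonferroni multiple hypothesis correction will be utilized (four outcome metrics"), and then "our corrected significance level for comparison is 0.0125 (0.05 divided by the four hypotheses tested"). No step-down or other sequential rule is mentioned, so each metric faces the same threshold whatever the other three show.

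Two other SAP sections bear on the point:

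- Reported Outcomes: "We will also report the 95% confidence interval for the differences between FES and noFES outcome metrics". No multiplicity adjustment of these intervals is stated.
- Power Analysis: "we require eighteen or more participants" "to achieve 80% power to reject the null hypothesis", "with a significance level (alpha) of 0.05". It adds: "An effect size of 0.7 was used for the power analysis".

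**The concern.** Bonferroni charges the last metric tested as much as the first. Once one null hypothesis has been rejected, at most three true nulls can remain, so the remaining tests no longer need a threshold of 0.05/4. Holm's procedure uses this fact; single-step Bonferroni leaves that part of the error allowance unspent.

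The usual reason to keep Bonferroni is that it comes with matching simultaneous intervals, here at 1 − 0.0125 = 98.75%. The SAP does not use that advantage, because it reports 95% intervals.

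What is at stake is the number of individual gait effects that can be declared. Each metric is tested as its own hypothesis, in a small sample, at a threshold four times stricter than the one used to size the study. A gain in power per metric that costs nothing is worth having in that setting.

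**Working it through.** **Inputs from the SAP.** Four metrics, family-wise alpha 0.05, per-metric alpha 0.0125, paired t-test, n = 18, effect size 0.7, power 80%.

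**Assumptions.**
- Tests are two-sided. The SAP does not say so, but its null hypothesis "states there is no difference between pre-test (noFES) and post-test (FES) conditions".
- 0.7 is the mean paired difference divided by the standard deviation of the differences, and applies to every responding metric.
- The number of responding metrics runs from 0 to 4, and the correlation between metrics takes the values 0, 0.5 and 0.8. The documents give neither.
- The four metrics, which the available SAP text does not name, are fixed in advance.

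**1. The plan's own figures.** 0.05/4 = 0.0125, as stated. Paired t-test power comes from the non-central t distribution with n − 1 = 17 degrees of freedom and non-centrality 0.7 × √18 = 2.97. At two-sided alpha 0.05 it is 79.9%, so the stated 18 participants for 80% reproduces to rounding. At alpha 0.0125 it is 57.9%.

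**2. Validity of both methods.** For Bonferroni with four independent true nulls, the family-wise error is 1 − (1 − 0.0125)⁴ = 0.0491; under any dependence it is at most 4 × 0.0125 = 0.05. For Holm, suppose m₀ of the four nulls are true. The smallest p-value among them has rank at most 4 − m₀ + 1, so it meets a threshold of at most 0.05/m₀. The chance that any of m₀ true nulls has a p-value that small is at most m₀ × 0.05/m₀ = 0.05. No independence is needed, and any valid p-value will do, from the t-test or the Wilcoxon test.

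**3. Dominance.** Holm's thresholds are 0.05/4, 0.05/3, 0.05/2 and 0.05/1, that is 0.0125, 0.0167, 0.025 and 0.05. None is below 0.0125, so every metric that passes Bonferroni passes Holm. The first threshold is the same, so the two methods always agree on whether anything is rejected.

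**4. Size of the gain.** Simulation of four equicorrelated normal paired differences, n = 18, effect 0.7 in each responding metric, 100,000 trials per scenario. The entries are average power per responding metric. Bonferroni is 58% throughout.

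| Metrics responding | Holm, corr. 0 | Holm, corr. 0.5 | Holm, corr. 0.8 |
|---|---|---|---|
| 1 | gain 0.2 points or less | same | same |
| 2 | 60.8% | 60.5% | 60.3% |
| 3 | 64.7% | 64.1% | 63.4% |
| 4 | 70.3% | 68.9% | 67.2% |

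The gain is therefore about 2.5–3 points with two responding metrics, 5.5–7 with three and 9–12 with four. Higher correlation shrinks it at this effect size. No Bonferroni rejection was lost in any trial. With all four responding, the chance of declaring all four rises from 11–38% to 37–60%.

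**5. Sensitivity.**
- n = 20 (the 10 adults plus 10 children in the protocol's Table 1 for Session C): about 65% to 67–68%, 70–72% and 74–77% with two, three and four responding.
- All four responding, n = 18, other effect sizes: 0.3, about 9% to 10–12%; 0.5, about 29% to 34–36%; 1.2, about 98% to 99% or more.
- Unequal effects 0.7, 0.5, 0.3 and 0.1: average power about 24% to 26–28%.

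**6. Realised family-wise error.** At n = 18 and correlation 0.5 it rises from 2.4% to 3.7% with two true effects and from 1.3% to 3.2% with three. With no true effect the two methods coincide. Holm never exceeded 5%.

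**The case against.** The strongest reply is that the SAP already names a valid, transparent procedure, and that choosing another valid one is for the sponsor. It has several parts.

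- *One significant metric may be enough.* The SAP states a single general question about gait, and the power analysis speaks of one null hypothesis. If any one significant metric counts as success, Holm adds nothing. This stands as a condition. However, the SAP counts four hypotheses and tests each, so the metric-by-metric results are part of what it sets out to report.
- *The larger gains need three or four metrics at 0.7.* This also stands. The documents do not support a common 0.7, and the study cited for it concerns reaching and grasping, by its title. With two responders or unequal effects the gain is only a few points. The simulation also covers the t-test and not the switch to Wilcoxon. These matters affect the size of the gain and not its direction.
- *Holm has no simple matching intervals.* True. A 95% t-interval would exclude zero while Holm does not reject in 79.9 − 70.3 = 9.6% to 79.9 − 67.2 = 12.7% of cases per metric when all four respond. The current plan is further apart, at 79.9 − 57.9 = 22.0%. The sponsor could remove the conflict by keeping Bonferroni and reporting 98.75% intervals, and a switch to Holm gives up that option. As written, the SAP does not take it.
- *Timing.* Stimulation is not blinded, and the protocol (Data Storage, Monitoring and HIPAA) has the investigator and sponsor reviewing data weekly. A change that can only add rejections must be fixed before outcome comparisons are seen. This is a fair condition on the fix.
- *The main problem lies elsewhere.* Sizing at 0.05 and testing at 0.0125 leaves 57.9% power; 80% would take 26 participants. Holm does not repair this, and it remains a separate matter.

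**Conclusion.** The point holds as an improvement in efficiency; the Bonferroni rule in the SAP is correct. Holm gives the same family-wise guarantee from the same data and can only add rejections. At the plan's own effect size and 18 participants it adds roughly 2.5 to 12 points of power per metric when two to four metrics respond. It adds essentially nothing when one does, and nothing to the chance of at least one finding.

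The direction follows from the thresholds and needs no assumption. The size rests on two-sided paired t-tests, a common effect of 0.7, and assumed numbers of responding metrics and correlations. Even the best case, about 70%, stays below the planned 80%. The practical weight is modest, since the protocol's Statistical Analysis section says the study is not meant to support clinical inference.

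**What to change.** Replace the Bonferroni sentence in Tests of Statistical Significance with: *The four p-values will be tested with Holm's step-down procedure at family-wise alpha 0.05 (ordered thresholds 0.0125, 0.0167, 0.025, 0.05, stopping at the first non-rejection).* Report Holm-adjusted p-values: with the p-values ordered from smallest to largest, the adjusted value at rank j is the largest of (5 − i) × p₍ᵢ₎ over i ≤ j, capped at 1.

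The 95% intervals in Reported Outcomes can stay, and should be labelled as not adjusted for multiplicity. Make and date the change before any comparison of stimulated with unstimulated walking is examined.

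The cost is one SAP sentence, with no added participants, measurements or assumptions. Realised family-wise error moves closer to the 0.05 bound but stays within it, and the simple route to matching 98.75% intervals is given up.
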